#### Process outcomes

	Analysis		
Outcome	cohort	Description	Outcome variable
Code Sepsis activation	All ED	Percentage of ED patients at intervention site	cs_yn
rate	patients* †	with a Code Sepsis activation during post-	
		intervention analysis phase	
Code Sepsis sensitivity	Sepsis	Percentage of ED patients at intervention site	cs_yn
	patients* †	with a sepsis during post-intervention analysis	
		phase for whom Code Sepsis was activated	
Code Sepsis PPV for sepsis	All ED	Percentage of Code Sepsis activations during	sepsis_yn (among
	patients* +	post-intervention analysis phase who met	= 1)
		sepsis criteria in the ED	

Outcome	Analysis cohort	Description	Outcome variable
Code Sepsis PPV for infection	All ED patients* †	Percentage of Code Sepsis activations during post-intervention analysis phase who had infection on final assessment	infected (measured among patients with cs_yn == 1)
Door-to-Code Sepsis time	All ED patients* †	Time from ED arrival to Code Sepsis activation	cs_elapsed

\* Restricted to subset of cohort patients presenting to intervention hospital during post-intervention analysis phase.

+ Analyses will use all patients meeting criteria for cohort but disregard the exclusion for subsequent eligible encounter.

Sensitivity analyses will be based on the cohort excluding subsequent eligible encounters.

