#### 3.7.2 Secondary outcomes

- Clinical/patient-centered secondary outcomes (measured among all ED sepsis patients):
  - 1) All-cause mortality to day 30
  - 2) All-cause mortality to 1 year
  - 3) In-hospital all-cause mortality
  - 4) Hospital charges: Amount charged to patient for their medical care during index ED visit and associated hospitalization.
  - 5) Hospital length of stay
- Process/feasibility secondary outcomes
  - 1) Code Sepsis activation rate: Measured as the percentage of all ED patients for whom the Code Sepsis protocol was activated.
  - 2) Code Sepsis activation accuracy metrics. Accurate Code Sepsis activation is defined as activation for patients who have sepsis while in the ED and no activation for patients who do not have sepsis in the ED.
- Adverse effects and unintended outcomes of protocol implementation

- 1) Antibiotic utilization percentage: measured as the fraction of (1) all ED patients; (2) Code Sepsis activation patients; or (3) "likely" sepsis patients who received IV or IV-equivalent antibiotics.
- 2) Antibiotic spectrum: Total Stenehjem antibiotic spectrum score for all antibiotics administered in first 24 hours, measured for (1) all ED patients or (2) sepsis patients
- 3) Antibiotic overtreatment rate: Percentage of "sepsis mimic" patients who received IV or IVequivalent antibiotics in the ED.
- 4) New onset C. difficile colitis incidence: Percentage of (1) all ED patients and (2) ED sepsis patients with a positive stool test for *Clostridium difficile* colitis between 72 hours and 90 days after ED arrival.
- 5) Adverse drug & allergic reaction incidence: Measured as the fraction of 1) all ED patients and (2) ED sepsis patients with a discharge diagnosis code consistent with anaphylaxis or with an adverse reaction to antibiotics (see Appendix C).
- Potential exploratory outcomes
  - 1) Measures of organ failure trajectory, to include change in the SOFA score between hospital day 1 and hospital day 3, and overall and organ-specific measures of organ failure-free days through day 28.

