- 5) Proceed with next therapeutic and/or diagnostic steps including, for confirmed sepsis patients, immediate initiation of an appropriate antibiotic regimen chosen from a range of options contained in a Code Sepsis antibiotic pack brought to the bedside by a pharmacist on protocol activation. Code Sepsis antibiotic regimens have been selected based on published guidelines and local antibiotic resistance patterns with input from ED clinicians, pharmacists, and infectious disease/antibiotic stewardship personnel.
- 6) If initial huddle pronounced sepsis status as "indeterminate," return to step #4 after additional 20-25 minutes to follow up on additional diagnostic results (e.g. urinalysis, complete blood count
- 7) For antibiotic-treated patients, follow-up by antibiotic stewardship pharmacist active de-escalation or cessation as appropriate.

Additional protocol elements/details:

- Code Sepsis team members:
  - ED attending physician +/- ED resident physician or medical student
  - ED triage nurse
  - ED unit coordinator (i.e. unit secretary)
  - o ED nurses x2
  - o ED patient care technician
  - ED phlebotomist x1-2
  - ED pharmacist as available
  - o ED X-ray technician
- Code Sepsis electronic order entry: Code Sepsis order sets for diagnostic evaluation and antibiotic treatment will be constructed and activated at the intervention ED's electronic medical record with the beginning of study Phase #2. Order sets will help speed up diagnostic testing and treatment initiation, aid care standardization, and facilitate Code Sepsis event tracking and data collection.
- Code Sepsis clinical team training: With active support from intervention hospital clinical leadership as well as Intermountain's system-wide ED leadership team, the Code Sepsis ED Implementation Team will provide clinical staff in the implementation ED with training on the Code Sepsis protocol during the months prior to study Phase #2. Primary training will include distribution of instructional materials, direct education at clinical staff meetings, targeted in-person education, and *in situ* simulation. Primary training will complete early in study Phase #2, with consolidation training, protocol reminders, physician detailing, and targeted clinician reeducation continuing through study Phase #3.

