# Inclusion/exclusion criteria

Cohort	Inclusion	Exclusion	Cohort eligibility indicator variable*
ED sepsis cohort (primary analysis cohort)	
 
(1) Age ≥18 years
 
(2) Arrival to an intervention or control ED during study period
 
(3) Met all Sepsis-3 criteria in the ED
 
Acute organ failure in the ED defined by SOFA score while in the ED ,≥2 points above baseline
 
Suspected or confirmed infection while in the ED, based on having both: 
 
i. Administration of ,≥1 IV or IV-equivalent antibiotics while in the ED for suspected infection (i.e. antibiotics not given for prophylaxis)
 
ii. Collection of ,≥1 body fluid cultures while in the ED
 
 
 
	
 
Trauma patient
 
Subsequent eligible ED visit with sepsis after first eligible encounter during an analysis window
 
	cohort_sepsis
All adult ED patients cohort	
 
(1) Age ≥18 years
 
(2) Arrival to an intervention or control ED during study period
 
	
 
Trauma patient
 
Received antibiotics within 6 hours prior to study ED arrival
 
Subsequent eligible ED visit after first eligible encounter during an analysis window
 
Left ED without evaluation or treatment
 
	cohort_all
Sepsis high-risk cohort	
 
Age ≥18 years
 
Arrival to an intervention or control ED during study period
 
First recorded temperature ≥38.0°C
 
First-recorded vital sign data meets ≥2 of:         
 
a. Systolic blood pressure <90 mmHg
 
b. Glasgow Coma Scale (GCS) score <15
 
c. Respiratory rate ≥22 breaths/min or oxygen saturation <85%
 
 
 
	
 
Trauma patient
 
Received antibiotics within 6 hours prior to study ED arrival
 
Subsequent eligible ED visit after first eligible encounter during an analysis window
 
Left ED without evaluation or treatment
 
	cohort_risk

Cohort	Inclusion	Exclusion	Cohort eligibility indicator variable*
Sepsis	(1) Age ≥18 years	(1) Trauma patient	cohort_mimics
mimic	(2) Arrival to an intervention or control ED during study period	(2) Received antibiotics	

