### Safety outcomes

	Analysis		
Outcome	cohort	Description	Outcome variable
Antibiotic utilization	All patient	Receipt of IV or equivalent antibiotics within 24	abx_24h
	cohort	hours of ED arrival	
Antibiotic utilization	Sepsis	Receipt of of receiving IV or equivalent antibiotics	abx_24h
	high-risk	within 24 hours of ED arrival	
	cohort		
Potential adverse effect	Sepsis	Antibiotic-related adverse event (a discharge	<pre>icd10_ae_summary</pre>
of antibiotics	cohort	diagnosis code consistent with anaphylaxis or	
		with an adverse reaction to antibiotics)	
Potential adverse effect	All patient	Antibiotic-related adverse event (a discharge	<pre>icd10_ae_summary</pre>
of antibiotics	cohort	diagnosis code consistent with anaphylaxis or	
		with an adverse reaction to antibiotics)	
New-onset C difficile	Sepsis	New positive stool test for Clostridium difficile	cdiff_72h_new_analysis
	cohort*	colitis between 72 hours and 90 days after ED	ineligible)
		arrival	
		* Excludes patients with a positive C. difficile	
		assay in the 14 days preceding ED arrival or	
		within 72 hours following ED arrival	

	Analysis		
Outcome	cohort	Description	Outcome variable
New-onset C difficile	All patient cohort*	New positive stool test for Clostridium difficile colitis between 72 hours and 90 days after ED arrival	cdiff_72h_new_analysis (missing if ineligible)
		* Excludes patients with a positive C. difficile assay in the 14 days preceding ED arrival or within 72 hours following ED arrival	
Antibiotic	Sepsis	Receipt of antibiotics in the ED among ED	abx_ed
overtreatment rate	mimic	patients with a primary hospital discharge	
	cohort	diagnosis of congestive heart failure or venous	
		thromboembolism	
False-positive	Sepsis	Final adjudicated infection status is "not	uninfected
presumptive infection	cohort	infected" among ED patients meeting sepsis	
diagnosis rate		criteria	

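### Code Sepsis sensitivity and PPV for sepsis are scored against a reference that contains two care steps made more likely by activation, so some missed sepsis can leave the sensitivity denominator

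*SAP*

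**What the plan says.** Under Process outcomes, the SAP computes sensitivity among intervention-site patients "with a sepsis during post-intervention analysis" phase, as the proportion with an activation. PPV for sepsis is the "Percentage of Code Sepsis activations during" the "post-intervention analysis phase who met" sepsis criteria in the ED. The same opening words begin the next row, PPV for infection, which counts activations in the "post-intervention analysis phase who had infection on final assessment"; that row does not use the ED sepsis criteria.

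The criteria are in the SAP's Inclusion/exclusion table: ED SOFA at least 2 above baseline, at least one of "IV or IV-equivalent antibiotics while in the ED for suspected infection", and at least one body fluid culture collected in the ED. Protocol 3.7.2 uses the same target: "Accurate Code Sepsis activation is defined as activation for patients who have sepsis while in the ED".

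Protocol 5.2 puts blood and urine sampling in the concurrent evaluation that follows activation. A huddle then classes sepsis as confirmed, disproven or indeterminate, and confirmed patients get "immediate initiation of an appropriate antibiotic regimen chosen from a range of options". Protocol 3.7.2 (exploratory outcomes) lists culture collection and antibiotic initiation among the steps timed from activation.

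Under Safety outcomes, the SAP also reports, for the sepsis cohort, how often "Final adjudicated infection status is" not infected.

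**The concern.** Sensitivity and PPV should show whether the trigger finds patients with sepsis. Here two of the three parts of the reference are care steps in the bundle being triggered, which is incorporation bias. The reference can be met because the patient was activated, or missed because the patient was not.

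The sensitivity side matters more. Protocol 8.1.3 names, as a risk for sepsis patients who are not activated, that suspicion is lower and diagnosis is delayed. If the delay runs past ED departure, the patient is outside the sepsis cohort and the trigger's miss goes uncounted. No other SAP row measures sensitivity against a different reference. The footnoted sensitivity analysis changes only the handling of repeat encounters.

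Activation accuracy is a named secondary outcome of a feasibility study, and Protocol 3.5 and 5 say that continuation or wider adoption is expected to depend on the results. Readers planning a similar trigger will take these percentages at face value.

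**Working it through.** The plan states no expected sensitivity or PPV, so there is no figure to reproduce. The only related number is the planning assumption in Protocol 2.4.9 and 7.3 that 30% of sepsis patients in the intervention ED are activated.

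**How each type of patient is scored**

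- Septic, not activated, first antibiotic or first culture after the ED: outside the denominator, although a trigger miss.
- Septic, not activated, treated and cultured in the ED: kept as a miss, correctly.
- Septic, activated, but not treated or not cultured in the ED: outside the sensitivity denominator, and a false positive in PPV for sepsis.
- Uninfected, activated, with SOFA rise, culture and antibiotic: a true positive in PPV for sepsis, and added to numerator and denominator of sensitivity.
- Uninfected, activated, with no SOFA rise or no antibiotic: a false positive, correctly.
- Uninfected, not activated, but meeting all three criteria: counted as a miss, which lowers sensitivity.

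**Sensitivity.** Let s be true sensitivity, and let a1 and a0 be the probabilities that an activated and a non-activated septic patient get both steps in the ED. Counting septic patients only:

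reported = s·a1 / (s·a1 + (1 − s)·a0)

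Take s = 0.30, borrowed from the planning figure, and a1 = 0.95. Both a1 and a0 are assumptions.

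- a0 = 0.95: 0.285 / (0.285 + 0.665) = 30.0%
- a0 = 0.90: 0.285 / (0.285 + 0.630) = 31.1%
- a0 = 0.80: 0.285 / (0.285 + 0.560) = 33.7%
- a0 = 0.70: 0.285 / (0.285 + 0.490) = 36.8%
- a0 = 0.60: 0.285 / (0.285 + 0.420) = 40.4%

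The bias vanishes when a1 = a0 and reverses if a0 is larger (28.9% at a0 = 1.0).

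**PPV for sepsis.** Let p be the true share of activations with infected sepsis, c the share of those captured in the ED, o the share of the remaining activations with a SOFA rise, and t the share of these both treated and cultured:

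reported = c·p + (1 − p)·o·t

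All inputs are assumed: p = 0.50, o = 0.3 to 0.5, t = 0.2 to 0.6. The second term runs from 0.5 × 0.3 × 0.2 = 0.03 to 0.5 × 0.5 × 0.6 = 0.15.

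- c = 1: 53% to 65%
- c = 0.95, matching a1 above: 0.475 + 0.03 to 0.475 + 0.15, or 50.5% to 62.5%

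**What the other rows recover.** PPV for infection removes the dependence on ED treatment but ignores organ dysfunction. The adjudicated not-infected rate covers the whole sepsis cohort and is not split by activation. Neither gives the share of activations with both organ dysfunction and infection.

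**The case against.** The opposing case has force on several points.

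- A reader might infer that activation itself delivers the antibiotic, so that any overtreated patient counts as a correct activation. The documents do not support that. The antibiotic step follows a huddle that can disprove sepsis, and a SOFA rise is also required.
- A reader might infer that PPV is left uncorrected altogether. PPV for infection and the adjudicated not-infected rate already expose much of the overtreatment problem; what remains is the missing combined measure.
- A reader might infer that both measures must flatter the intervention. Direction is not guaranteed: uninfected non-activated patients who meet the criteria lower reported sensitivity, and septic activations not treated in the ED lower reported PPV.
- The reference is the study's prespecified ED definition. The current sensitivity row answers a legitimate question, namely what share of the primary-analysis population got the intervention. The 30% planning figure is closer to that quantity than to true sensitivity, so it serves only as a starting value.
- Protocol 8.3.4 (overtreatment and anchoring bias) says openly that the prediction tool was not meant to capture every septic patient.

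All of this narrows the point. None of it returns to the sensitivity denominator the septic patients first treated or cultured after ED departure.

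**Conclusion.** The point holds in limited form. Sensitivity and PPV for sepsis share two components with the bundle under test, and the sensitivity row has no companion measure that is less dependent on ED treatment. Sensitivity is overstated if activated septic patients are more likely than non-activated ones to get both an antibiotic and a culture in the ED. That is plausible from Protocol 5.2 and 8.1.3, but the documents do not quantify it. The 31% to 40% range depends on assumed capture rates and ignores uninfected patients; the PPV range rests wholly on assumptions.

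A reader might also take this as a threat to the main result. It is not: these are single-site, single-phase descriptive percentages with no hypothesis test, and the primary difference-in-differences test is untouched. The change is worth making because it is cheap and the accuracy figures may inform adoption.

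**What to change.** In SAP Process outcomes:

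1. Add a PPV for infected sepsis: the share of activations with ED SOFA at least 2 above baseline and a final infection status of infected.
2. Add a second sensitivity row. Its denominator is intervention-site, post-intervention patients with ED SOFA at least 2 above baseline plus an antibiotic and a culture within 24 hours of ED arrival, in the ED or on the ward. No new adjudication is needed.
3. Keep the current rows, labelled as measured against the study's ED sepsis cohort, that is, as coverage of the primary-analysis population.

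The cost is SAP wording and derived variables. Protocol 6.5 already lists SOFA, baseline SOFA, and antibiotic and culture times; the SAP already plans 24-hour antibiotic receipt and final infection status for activations.

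State the limits with the results. The 24-hour window reduces dependence on treatment but does not remove it. Septic patients never treated are still lost. Some infections or cultures arising after the ED stay may enter, and without adjudication uninfected patients remain in the new denominator.

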### Data analysis

Analyses for causal inference regarding primary, secondary and safety outcomes will employ a quasi-experimental method called *difference-in-difference* (DID) analysis to control for secular trends and confounding of unknown individual factors associated with the outcome of interest. The DID approach will provide an estimate of the effect of the Code Sepsis intervention on primary, secondary, and safety outcomes by comparing the intervention and control hospitals during the pre- and post-implementation periods (Figure 1).

For the primary outcome, DID analysis will use multivariable linear regression to compare the adjusted mean door-to-

antibiotic time (primary outcome) at the intervention hospital

pre- versus post-implementation of the Code Sepsis protocol using the measured change at contemporaneous control non-intervention hospitals to control for pre-/post-intervention changes not attributable to protocol implementation after adjustment for potential confounders.

The following equation will be used to estimate the adjusted mean differential change in the primary outcome, door to antibiotic time:

$$Y_{igt} = \beta_0 + \beta_1 Int_g + \beta_2 Post_t + \beta_3 (Int_g * Post_t) + \beta_4 Cov$$

Where  $Y_{igt}$  is the door-to-antibiotic time for patient *i* treated at an intervention or non-intervention ED *g* at pre- or post-intervention time *t*. *Int* is a binary indicator for the subject being treated at an intervention hospital; *Post* is a binary indicator the post-intervention period; and *Cov* represents a vector of patient-level covariates. The  $\beta_3$  parameter from the regression model presented above estimates the adjusted mean differential change in door-to-antibiotic time observed in the Code Sepsis intervention hospital compared to the control hospital. We will consider the Code Sepsis intervention to have had an impact if  $\beta_3$  is statistically significant and different from zero.

The parallel trend assumption will be tested using the approach outlined by Callaway and Sant'Anna. This approach allows for testing the parallel trend assumption after conditioning on covariates. This approach is

limited in that it only considers the control and treated groups during the pre-implementation phase. If the pre-test of parallel trends assumption fails, then we will weight the gamma regression model with propensity scores. As demonstrated by Stuart *et. al*, this will balance the covariates amongst the four study groups defined by their treatment status as well as time (pre vs post). We will leverage the covariate balancing propensity score (CBPS) library in R to generate propensity scores. This weighting approach can recover treatment effects in that it allows for adjustments due to observed baseline covariates that differ either across groups or over time. Covariates that will be used in generating propensity scores will include age; sex; weighted Elixhauser comorbidity score; English language preference; first-available heart rate, temperature, systolic blood pressure, and respiratory rate; acute physiology score; ED arrival at nightime (10 pm to 6:59 am), ED arrival on weekend (midnight Saturday to 11:59 pm Sunday), SARS-CoV-2 test result (positive, negative, or not performed during ED-associated hospitalization or within 14 days preceding ED arrival); and insurance type. For analyses involving a cohort of patients with sepsis, propensity score covariates will additionally include arrival to ED via ambulance; presentation from a long term care facility; serum lactic acid level checked and ≥2 mmol/dL; ED SOFA score; and ED-diagnosed infection source.

In order to account for the right skew known to exist in door-to-antibiotic time we will use generalized linear gamma regression to estimate the DID. Evaluation of secondary outcomes will employ an analogous approach using multivariable linear, Poisson, logistic, or gamma regression as appropriate. Data from the wash-in phase will be excluded from DID analyses. All multivariable models will be adjusted for demographic and clinical parameters with known or plausible associations with both outcomes and treatment hospital, presentation before or after Code Sepsis implementation, and/or Code Sepsis activation as well as select precision variables as detailed below. Analyses for secondary, safety, and heterogeneity of treatment effect outcomes will not be adjusted for multiple comparisons and will therefore be considered hypothesis generating.

Statistical significance will be set to p < 0.05. All analyses will be conducted with R.

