## 7. DATA ANALYSIS

#### 7.1 Introduction to Quasi-Experimental Analysis

This study will measure the effect of implementing a teambased Code Sepsis protocol for ED sepsis patients by comparing risk-adjusted process and patient-centered outcomes before versus after protocol implementation at a single hospital. Results from simple pre/post analyses, however, may be subject to misinterpretation due to *secular trends* (changes in the measured outcomes over time not attributable to the study intervention). Analyses of Aim III primary and secondary outcomes will therefore employ quasi-experimental methods to eliminate confounding due to secular trends when estimating the effect of Code Sepsis implementation on outcomes. More complex methods of quasi-experimental analysis includes interrupted time series

Figure 4. Difference-in-differences analysis

and regression discontinuity, but are analogous to the relatively simpler approach called *difference-in-difference analysis* (Figure 4). Difference-in-difference analysis uses multivariable linear regression to compare the adjusted mean door-to-antibiotic time (primary outcome) at the intervention hospital preversus post-implementation of the Code Sepsis protocol using the measured change at non-intervention hospitals to control for pre-/post-intervention changes not attributable to protocol implementation.

 $Y_i = \beta_1 \text{ERA}_i + \beta_2 \text{HOSP} + \beta_3 \text{ERA}_i \times \text{HOSP}_i + \beta_4(Z_i)$ Figure 5. Simplified difference-in-differences equation.  $Y_i$  is the door-toantibiotic time for patient *i*, HOSP and ERA are, respectively, indicator variables for care at the intervention hospital or an ED arrival date after Code Sepsis implementation, and Z is a vector of covariates.  $\beta_3$  is the coefficient of interest.

This model tests the *difference* in intervention ED versus non-intervention EDs' *differences* in outcome before versus after the Code Sepsis implementation (Figures 4-5). The  $\beta_3$  parameter from the regression model depicted in Figure 5

provides the adjusted difference-in-differences estimate and significance tests for the influence of the Code Sepsis intervention on the outcome of interest.

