### Study overview

To assess feasibility and test the preliminary effects of ED-based Code Sepsis teams on care delivery and patient outcomes, we will conduct a Phase 2a implementation trial involving Code Sepsis team activation in one ED while collecting contemporaneous control data at two other urban EDs (control sites). Application of pseudo-experimental analysis methods to collected data will facilitate causal inference.

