#### Heterogeneity of treatment effect for primary outcome

Potential heterogeneity of treatment effect (HTE) will be evaluated using a differences-in-differences-indifferences approach adding interaction terms for subgroups versus study phase and versus control/intervention ED, and a three-way interaction between subgroup, study phase, and control/intervention ED. Subgroup results will be considered descriptive and will be referenced to the overall treatment effect from the primary analysis. The subgroup analyses are not confirmatory, hence no corrections for multiple comparisons will be made.

The following are predefined subgroups for HTE analyses:

- Age (<65 years vs ≥65 years)
- Sex (male vs female)
- Presence of hypotension on ED arrival (SBP <90 or MAP <65)
- Arrival to hospital via ambulance
- Source of infection
- APS quartiles

We will use the following DID formula for HTE analyses:

$$Y_{igts} = \beta_0 + \beta_1 Int_g + \beta_2 Post_t + \beta_3 Sub_s + \beta_4 (Int_g * Post_t) + \beta_5 (Post_t * Sub_s) + \beta_6 (Post_t * Int_g * Sub_s) + \beta_7 Cov$$

Where  $Y_{igts}$  is the door-to-antibiotic time for patient *i* treated at an intervention of non-intervention ED *g* at pre- or post-intervention time *t* from the cohort subgroup *s*. *Int* is a binary indicator for the subject being treated at an intervention hospital; *Post* is a binary indicator the post-intervention period; *Sub* is a binary indicator (or group indicator in the case of APS quartiles) of the subgroup; and *Cov* represents a vector of hospital- and patient-level covariates. The  $\beta_6$  parameter from the regression model presented above estimates the effect measure modification for door-to-antibiotic time in pre-specified subgroups. We will consider the Code Sepsis intervention to have had an impact on the subgroup if  $\beta_6$  is statistically significant and different from zero.

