### Power

It was estimated that the intervention ED provides care for 1,650 sepsis patients annually (approximately 4.5 sepsis patients per day) and the control EDs together care for a total of 2,200 sepsis patients annually (approximately 6 sepsis patients per day). Estimated control door-to-antibiotic time for ED sepsis patients was an average 170 (±75) minutes based on 2013-2017 data from study hospitals, with approximately 5-10% of patients receiving antibiotics within 1 hour of ED arrival. Based on these assumptions, we estimated 90% power to detect a difference-in-differences change of 16 minutes or more in door-to-antibiotic time associated with Code Sepsis implementation, with the measurement population being all ED sepsis patients. Power calculations employed Monte Carlo simulations.

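### The primary model gives the two control EDs one shared intercept, so a change in each ED's share of control patients between phases could bias beta3 in either direction

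*SAP*

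**What the plan says.** The SAP (Study overview) and Protocol 4.1 name one intervention ED and two control EDs. The primary equation in the SAP's Data analysis section contains Int, Post, Int by Post and covariates.

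- Int "is a binary indicator for the subject being treated at an intervention hospital".
- Cov "represents a vector of patient-level covariates".
- Beta3 is read as the differential change "in the Code Sepsis intervention hospital compared to the control hospital", with the controls treated as a single unit.

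The 11 adjustment covariates for primary and secondary outcomes include no hospital term. Neither do the safety covariates, the propensity-score covariates or the multi-group interrupted time-series equation (Sensitivity analyses). Protocol 7.1 has the same structure, with "indicator variables for care at the intervention hospital" and for the post-implementation era. In the subgroup section Cov "represents a vector of hospital- and patient-level covariates", but no hospital-level covariate is named. Study site is used in the imputation model (Missing data) and in no outcome model.

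The decision rule is that beta3 differs significantly from zero: "Statistical significance will be set to p < 0.05".

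**The concern.** The control change is the counterfactual for the intervention hospital. With one intercept for two hospitals, the pooled control mean can move between phases when neither hospital's own mean has changed, simply because one contributes a larger fraction of the control patients. The model assigns that movement to Post, and it reaches beta3 with the opposite sign. A shift towards the slower control ED looks like a benefit of Code Sepsis; a shift towards the faster one hides a benefit.

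The planned safeguards do not cover this. The SAP itself says that the parallel-trends test looks only at the pre-implementation phase, so it cannot see a pre-to-post change in shares. The propensity-score fallback starts only if that test fails, and it balances the listed covariates, which do not include hospital. The key time-series sensitivity model also pools the two EDs.

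**Working it through.** **Inputs from the documents.** Mean (SD) door-to-antibiotic time 170 (75) minutes, pooled over study hospitals; 1,650 sepsis patients a year at the intervention ED and 2,200 at the control EDs together (Protocol 7.3; SAP Power). Each analysis phase lasts 12 months (Protocol 4.2.5). Two-sided 5% is assumed, since the SAP does not state sidedness.

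**Inputs not in the documents.** The door-to-antibiotic time at each control ED, the split of the 2,200 patients, and that split by phase. The gap and the share shift below are therefore assumptions.

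**The plan's own figure.** The SAP says "we estimated 90% power to detect a difference-in-differences change of 16 minutes or more in door-to-antibiotic time". A four-cell normal approximation gives:

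- SE = 75 x sqrt(2/1,650 + 2/2,200) = 3.45 minutes.
- Power at 16 minutes = Phi(16/3.45 - 1.96) = 99.6%; 90% power is reached at 11.2 minutes.
- If the annual counts are instead split over both phases (825 and 1,100 per cell), SE = 4.89 minutes and power = 90.6%.

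The 90% does not follow from the annual counts as written. The stated figure is the cautious one, the Monte Carlo details are not in the documents, and nothing below depends on it.

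**Bias formula.** Let control ED A be slower than control ED B by an adjusted gap g, and let A's share of control patients be p0 before and p1 after. The control change is the true change plus (p1 - p0) x g. Hence:

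bias in beta3 = -(p1 - p0) x g

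It is zero if either factor is zero.

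**Size**, with type I error = Phi(-1.96 + b/3.45) + Phi(-1.96 - b/3.45) for absolute bias b:

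| Adjusted gap (min) | Share shift (points) | Bias, absolute (min) | % of 16 min | Type I error |
|---|---|---|---|---|
| 0 | any | 0 | 0 | 5.0% |
| 10 | 5 | 0.5 | 3% | 5.2% |
| 20 | 5 | 1.0 | 6% | 6.0% |
| 20 | 10 | 2.0 | 12.5% | 8.9% |
| 30 | 10 | 3.0 | 19% | 14% |
| 40 | 15 | 6.0 | 37.5% | 41% |

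**Simulation check.** Gamma outcomes were generated with mean about 170, SD about 75 and no true effect. The slower control ED started with 57% of control patients, a share borrowed from annual ED visits: 65,000 / (65,000 + 49,000).

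- Linear model, 30-minute gap, 10-point shift (1,000 runs): mean beta3 was -3.0 minutes with 12.8% false positives without a hospital indicator, and 0.0 minutes with 4.9% with one.
- Linear model, 20 minutes and 5 points: -0.9 minutes and 5.5% without; 0.1 minutes and 4.6% with.
- Log-link gamma model, 30 minutes and 10 points (300 runs): log ratio -0.019 and 14% without; -0.002 and 6% with.

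**The case against.** **Measured case mix is already adjusted for.** A reader might infer that any shift in patient mix at the control EDs passes into beta3. The documents do not support that. Age, comorbidity, long-term care, arrival mode, language, temperature, blood pressure, acute physiology score, SOFA score and infection source are in the model. What gets through is the change in each ED's share multiplied by the gap that remains after adjustment. This objection stands, and the formula uses the adjusted gap for that reason.

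**Neither ingredient is shown.** A reader might infer that the result will be biased, or that Code Sepsis will be falsely credited. The documents report no gap and no shift, and the sign is open. Some facts point to small values. Both control EDs are regional referral sites (Protocol Table 1), all sites share a care process model, checklist and order sets (Protocol 5.1), and two full 12-month phases make season alone an unlikely cause of a shift. Others point the other way. The control EDs differ in volume and ED beds (49,000 visits and 28 beds; 65,000 and 35). Protocol 3.1 reports five-fold variation between physicians in median door-to-antibiotic time and delay when the ED is busy, while staffing and crowding are not covariates. The post phase runs from February 2020 to February 2021, and SARS-CoV-2 result is a propensity-score covariate but not one in the primary list. The range must include zero, but zero cannot be assumed.

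**The bias is small beside the hoped-for effect.** The planning inputs imply 0.30 x (170 - 50) = 36 minutes averaged over all sepsis patients, and even 6 minutes would not overturn an effect of that size. This stands. The exposure is to the 5% error rate and to effects near the detectable limit.

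**The subgroup wording.** A reader might infer that the subgroup model has hospital covariates which the primary model lacks. It names none, and the SAP says that its patient-level list also serves the subgroup analyses. This is better read as loose wording.

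**Conclusion.** The structural point holds: no outcome model specifies a term that separates the two control EDs, so a change in their shares of control patients enters beta3 in proportion to their adjusted gap, and no planned check would reveal it. Under assumed gaps of 0 to 40 minutes and shifts of 0 to 15 points the bias is 0 to 6 minutes in either direction. Six minutes needs both upper assumptions at once; up to 20 minutes and 10 points it is at most 2 minutes. The error rates assume independent patients, SD 75 and the annual counts in each phase.

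A reader might also infer that hospital effects would make the comparison secure. They remove only a time-constant gap between the control EDs. They do not remove unmeasured change in case mix within a hospital. If the control EDs trend differently, beta3 still depends on how they are weighted. Inference from one treated and two control sites remains open. This is a low-cost improvement to make before analysis, not evidence that the primary result will be wrong.

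**What to change.** - **Primary, secondary and safety difference-in-differences models:** replace the Int main effect with hospital indicators and keep intervention hospital by Post as beta3. Cost: one extra parameter, against about 2 x (1,650 + 2,200) = 7,700 planned sepsis patients.
- **Interrupted time-series model:** its equation has no Int main effect to replace, so add hospital indicators (two parameters).
- **Subgroup models:** add hospital indicators, with hospital-by-subgroup terms if the gap between the control EDs differs by subgroup. State which hospital-level covariates are meant, or delete the phrase.
- **Reporting:** give each control ED's patient count by phase, so that any share shift is visible. Report beta3 against each control ED separately as a descriptive sensitivity analysis. This is less precise: with an assumed equal split of 1,100 per phase, SE = 75 x sqrt(2/1,650 + 2/1,100) = 4.13 minutes instead of 3.45.

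No new data are needed, since the SAP expects study hospital and phase to be complete for every encounter. The limits of hospital effects given in the verdict should be stated with the results.
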